4 STUDY DESIGN

4.1 OVERALL DESIGN

This is a Phase Ib-IIa, randomized, double blinded, placebo controlled clinical trial of orally administered Tofacitinib, 5 mg twice daily, for treatment of individuals with mild to moderate SS disease activity. The study will aim to screen up to 76 adult participants in order to achieve a target study of 30 participants for randomization plus up to 11 participants to replace subjects lost to attrition or early withdrawal from the study and to complete enrolment in unfilled randomization blocks. There will be two (2) study arms with 20 participants in Tofacitinib arm and 10 participants in placebo arm. The study duration is a maximum of 241 days with a 45-day screening period followed by a 168-day treatment period and a 28-day follow-up period. The study is a single-site study to be conducted in the NIH Clinical Center. The proposed clinical trial is an exploratory study designed to yield preliminary data about the safety, clinical, and biologic efficacy of Tofacitinib in SS participants with mild to moderate disease activity.

4.2 SCIENTIFIC RATIONALE FOR STUDY DESIGN

The proposed clinical trial is an exploratory study designed to yield preliminary data about the safety, and clinical and biologic efficacy of Tofacitinib in SS participants with mild to moderate disease activity. If the drug is well tolerated by SS participants, the data can be used to design and power a larger study of clinical efficacy and safety.

4.3 JUSTIFICATION FOR DOSE

As per the package insert recommendations, each participant will be dosed with 5 mg (1 tablet) twice daily for 168 days as is recommended for the treatment of rheumatoid arthritis.

Tofacitinib and placebo tablets will be supplied by Pfizer Incorporated to the NIH Clinical Center Research Pharmacy.

5 STUDY POPULATION

5.1 INCLUSION CRITERIA

Adult primary SS participants with mild-to-moderate disease activity will be eligible for this study. Enrolled participants can be naïve or failed immunosuppressive therapy beyond antimalarials and glucocorticoids; to prevent bias in the cohort of participants with more recalcitrant disease. We expect that Tofacitinib is a potential second line therapy, in addition to antimalarials and glucocorticoids, depending on the participant's initial presentation and response. Women and members of minority groups, if eligible, will be included in accordance with the NIH Policy on Inclusion of Women and Minorities as Participants in Research Involving Human Participants.

In order to be eligible to participate in this study, an individual must meet all of the following criteria:

1. Ability of participant to understand and the willingness to sign a written informed consent document.
2. Participation and enrollment in companion protocol, 15-D-0051, Characterization of Diseases with Salivary Gland Involvement.
3. Stated willingness to comply with all study procedures and availability for the duration of the study
4. Male or female, aged between 18-75 years
5. In good general health as evidenced by medical history
6. Meets the 2002 American European Consensus Group classification criteria for primary Sjögren's Syndrome or 2016 American College of Rheumatology/European League against Rheumatism Classification Criteria (ACR-EULAR) with mild to moderate disease activity defined as ESSDAI between 0 to 13 at the screening visit and >0 ml/min/gland stimulated saliva flow.
7. Ability to take oral medication and be willing to adhere to the study intervention regimen
8. If on glucocorticoids, the dose must be less than 10 mg daily and stable for the 4 weeks (28 days) prior to screening visit.
9. If on hydroxychloroquine or other antimalarials such as chloroquine or quinacrine, the dose must have been stable for the 12 weeks (96 days) prior to screening visit. The maximum allowed dose is hydroxychloroquine up to 400 mg/day or 6.5 mg/kg/day if more than 400 mg/day. The maximum allowed dose for chloroquine phosphate is up to 500 mg daily and for quinacrine up to 100 mg daily.
10. Participants may be on lipid lowering medications if initiated at least 3 months prior to the screening visit and dose must be stable for 4 weeks (28 days) prior to study entry.
11. Males and females with potential for reproduction must agree to practice effective birth control measures. Females should be on adequate contraception if they are of child-bearing potential documented by a clinician, unless participants or spouse have previously undergone a sterilization procedure. Adequate birth control measures are: intrauterine device (IUD) alone or hormone implants, hormone patches, injectable, or oral contraceptives plus a barrier method (male condom, female condom or diaphragm), abstinence or a vasectomized partner.

12. Agreement to adhere to Lifestyle Considerations (see section 5.4) throughout study duration

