6.3 MEASURES TO MINIMIZE BIAS: RANDOMIZATION AND BLINDING

Randomization will be done by the NIH Clinical Research Center Pharmacy in conjunction with the statistician associated with the study. This is a two-arm, double blind study.

The study will utilize the stratified block randomization method to ensure that the Tofacitinib and placebo groups are balanced with respect to the baseline disease activity level. Eligible

Abbreviated Title: Tofacitinib in Sjögren's syndrome

Version Date: 07/01/2024

subjects will be stratified according to the ESSDAI score (0-1 vs. 2-13). Within each stratum, subjects will be randomly assigned by use of computer-generated blocks of size 3 with a 2:1 ratio to Tofacitinib or control group. Thus, participants will be randomized to either Tofacitinib or placebo in a 2:1 ratio overall. Both participants and investigators will be blinded to treatment allocation. Unblinding for analysis will occur once all the collected study data has been entered and the database is locked. Participants and local treating physicians will be informed of treatment allocation by a letter sent by certified mail, at that time.

The blind will be held by the statistician and the NIH Clinical Center Research Pharmacy. In cases where breaking the blind is necessary to provide clinical care to the participant, as determined by the PI and medically responsible team member, [name], the PI will contact the NIH Clinical Center Research Pharmacy and provide the treatment allocation information to the treating physician. Such participant(s) would be withdrawn from the study and followed up as described in section 4.10 above.

The Data and Safety Monitoring Committee (DSMC) may also request unblinding of treatment allocation or group assignment. These requests will be transmitted to the NIH Clinical Center Research Pharmacy by the PI. Data will be provided directly to the DSMC Chair without unblinding the investigators before the DSMC determines a plan of action.

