9.1.1 SAMPLE SIZE DETERMINATION

This is a pilot, Phase Ib-IIa study intended to study predominantly the tolerability/toxicity of Tofacitinib. The number of participants for this study is arbitrary and is based primarily on the conventional numbers in Phase II studies and our experience with similar studies conducted previously. The primary endpoint is safety and tolerability. 15- 20 participants are commonly used as the sample size for open label safety studies. Our plan to have 20 Participants dosed with Tofacitinib to evaluate for safety and a placebo group of additional 10 participants for comparison is consistent with Phase I studies.

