9.3 STATISTICAL ANALYSES

9.3.1 General Approach

Demographics and clinical variables will be summarized by treatment group for each study visit. For continuous variables, descriptive statistics includes mean, standard deviation, median, and range. For categorical variables, counts and percentages will be reported. Due to exploratory nature of this study, statistical testing will be performed at the two-sided 5% level for the efficacy variables. The 95% confidence interval will be provided as well.

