9.3.3 Analysis of the Secondary Endpoint(s)

Secondary endpoints listed in Section 3.0 will be analyzed for the ITT population. Continuous endpoints (e.g. change from baseline (Day 1) to end of treatment (Day 168) will be compared between treatments using analysis of covariance (ANCOVA) model with baseline as a covariate if normality assumption holds. Otherwise, the nonparametric alternative will be adopted. For repeated measures, linear mixed models will be used. For multi-omics data, transcriptional pathway analysis, graphical data visualization (heat maps, cluster analysis), and differential gene expression analysis will be performed.

Secondary endpoints will be analyzed by comparisons between the treatment (all SS participants receiving Tofacitinib) and placebo groups once the last participant completes the 28 weeks (196 days) of study.

- Change in the ESSDAI score between baseline and Day 168 (end of treatment).
- Change in the Physician's Global Assessment (PGA) scores between baseline and study day 168 (end of treatment).

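### Randomisation separates ESSDAI 0-1 from 2-13, but the ESSDAI change analysis gives one pooled difference and does not use the strata

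*Combined protocol and SAP*

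**What the plan says.** - **Entry (5.1, criterion 6).** Eligible disease is "mild to moderate disease activity defined as ESSDAI between 0 to 13 at the screening visit". Zero is inside the range.
- **Randomisation (6.3).** Eligible "subjects will be stratified according to the ESSDAI score (0-1 vs. 2-13"), using "computer-generated blocks of size 3 with a 2:1 ratio to Tofacitinib or control group". No limit is set on the size of the 0-1 stratum.
- **Size (4.1, 9.1.1).** There are "two (2) study arms with 20 participants in Tofacitinib arm and 10 participants in placebo arm". Section 9.1.1 states that "The number of participants for this study is arbitrary" and gives no effect size, SD or power.
- **Analysis (9.3.3).** A listed secondary endpoint is "Change in the ESSDAI score between baseline and Day 168 (end of treatment"). It is analysed in the ITT population by ANCOVA with baseline as covariate, or by a nonparametric alternative. The section names no stratum term, treatment-by-stratum interaction or estimate within strata. The exploratory repeated-measures analysis of ESSDAI in Section 9.1 adds none.
- **Inference (9.1, 9.3.1).** Section 9.1 calls all analyses descriptive and exploratory, yet Section 9.3.1 says "statistical testing will be performed at the two-sided 5% level for the efficacy variables", with 95% confidence intervals.
- **Use (4.2).** If the drug is well tolerated, "the data can be used to design and power a larger study of clinical efficacy and safety".

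**The concern.** ESSDAI is the only composite disease activity index among the clinical secondary endpoints; PGA and salivary flow stand beside it. It is bounded below at 0, so participants in stratum 0-1 have almost no room to improve on it. The plan recognises this group when it randomises but not when it analyses. The single difference in Section 9.3.3 therefore mixes two groups with different scope for change, in a proportion set by who happens to enrol.

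Stratified allocation keeps that proportion similar in the two arms, and baseline as a covariate removes chance baseline differences. Neither separates the effect in one group from the effect in the other. A later trial that recruited only patients with scored activity could be sized on a figure that does not describe them, and a reader could not tell how much of a small difference came from the floor.

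**Working it through.** There is no power calculation to reproduce, because Section 9.1.1 gives no statistical inputs. What follows is an illustration.

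**From the documents:** 20 v 10 participants (4.1); 2:1 allocation within stratum (6.3); ITT ANCOVA on change (9.3.3).

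**Assumed:** share f in stratum 0-1 of 20%, 33% or 50%; an effect of 2 points in stratum 2-13 and 0 in stratum 0-1; SD of change 3 in stratum 2-13 and 0.7 to 1.5 in stratum 0-1.

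**Formulas**
- Pooled difference = (1 - f) × 2.
- Pooled SE = √{[(1 - f) × 9 + f × SD₀²] × (1/20 + 1/10)}, where SD₀ is the SD in stratum 0-1. This uses the average within-stratum variance.
- SE in stratum 2-13 = √{9 × [1/(20(1 - f)) + 1/(10(1 - f))]}.

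| f | Pooled difference | Pooled SE | SE in stratum 2-13 |
|---|---|---|---|
| 20% | 1.6 | 1.05-1.07 | 1.30 |
| 33% | 1.3 | 0.96-1.01 | 1.42 |
| 50% | 1.0 | 0.84-0.92 | 1.64 |

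At f = 50% with SD₀ = 0.7, the pooled variance is 4.5 + 0.245 = 4.745 and the SE is √(4.745 × 0.15) = 0.84. With SD₀ = 1.5 it is √(5.625 × 0.15) = 0.92. In stratum 2-13, with 10 v 5 participants, it is √(9 × 0.3) = 1.64.

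**Signal-to-noise at f = 50%.** Stratum 2-13 gives 2/1.64 = 1.22. The pooled analysis gives 1.0/0.92 = 1.09 to 1.0/0.84 = 1.19. The two are close.

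**Does baseline adjustment help?** An ANCOVA simulation with scores floored at 0 assumed a 3-point effect and SD 3 in stratum 2-13, baseline uniform on 2-13, and no drug effect in stratum 0-1. The mean estimated difference was -2.74, -2.14, -1.87 and -1.31 at f = 0, 20, 30 and 50%. Relative to f = 0, these are 78%, 68% and 48% (for example 1.31/2.74 = 0.48), close to 1 - f. Baseline as a main effect did not remove the dilution. The value of -2.74 rather than -3 at f = 0 shows that the floor also acts on low scores within stratum 2-13.

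**Consequence for sizing.** This applies only if the next trial enrolled patients like stratum 2-13 and used ESSDAI change. The standardised effect is 2/3 = 0.67 in that stratum. Pooled, it is 0.58-0.59, 0.51-0.54 and 0.42-0.46 at 20, 33 and 50%. Required size varies with the inverse square, so sizing on the pooled figure would inflate it by about 1.3, 1.5-1.7 and 2.1-2.5 times. If the next trial recruited the same mix, the pooled figure would be the relevant one.

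**The case against.** The case for leaving the plan alone has real force.

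- **Other measures exist.** Section 3 pairs PGA with ESSDAI in the same objective and lists salivary flow as a further secondary endpoint. A participant at ESSDAI 0 still informs both. A reader might infer that clinical improvement rests on ESSDAI alone; the documents do not say so.
- **Dilution by exactly the 0-1 share is not a fact.** It requires no drug effect in that stratum. Those participants can worsen, the plan counts flares, and less worsening on drug would be a genuine effect. Eligibility is also fixed at screening while change runs from Day 1, so a screening score of 0 need not be a baseline of 0. This stands, and it is why the point is conditional.
- **Reading only stratum 2-13 is not free.** At a 50% share the SE rises from 0.84-0.92 to 1.64. The signal-to-noise advantage disappears if the effect in stratum 0-1 is only about 0.05-0.24 points. With t distributions (13 v 28 degrees of freedom), power is 20% in the stratum and 18-21% pooled. This argues against making 2-13 the governing estimate. It does not argue against reporting it.
- **The use for sizing is general.** Section 4.2 speaks of the data as a whole. The measures tied by name to powering a larger trial are systemic biomarkers (synopsis and Section 3).
- **Section 3 counts an unchanged ESSDAI as meeting the objective.** On that reading someone who stays at 0 succeeds. That does not rescue the contrast, since it happens in either arm, and Section 9.3.3 analyses the change in score.
- **The trial is exploratory and safety is primary.** This limits the weight of the point, but efficacy tests and intervals are still planned.

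**Conclusion.** The point holds as a gap between randomisation and analysis: strata defined by ESSDAI are randomised on and then not used for ESSDAI. Where the drug has little effect on worsening in stratum 0-1, the pooled difference understates the effect in stratum 2-13 by roughly the 0-1 share. Under the illustrative assumptions a 2-point effect appears as 1.6, 1.3 or 1.0 points. The actual size cannot be known from the documents, because the share, effect and SD are not given. Pre-screening looks for mild-to-moderately active disease (8.1.1), so the share may be small.

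Two stronger readings are not supported. One is that criterion 6 is wrong and entry should be narrowed: the primary aim is safety, and low-activity participants contribute to it. The other is that the ITT estimate should give way to stratum 2-13: that group may number about 15 at a 50% share. No stated power is invalidated, since none is stated, and the adverse event analysis is unaffected. This is a low-cost improvement to an exploratory analysis.

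**What to change.** Amend Section 9.3.3, before unblinding, to:

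1. Include the randomisation stratum (0-1 v 2-13) in the ESSDAI model with baseline ESSDAI, keeping the ITT estimate.
2. Prespecify, beside the ITT estimate, the number of participants and the ESSDAI change to Day 168 with 95% confidence interval by arm within each stratum. For stratum 0-1, also show worsening and flare by arm.
3. State that both the pooled and the 2-13 estimates, with their intervals, will be considered when sizing a later trial.

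Eligibility, randomisation, visits and safety analyses do not change. The cost is a few lines of text and one table from strata already recorded. The stratum term alone does not separate the two effects; the estimates by stratum do that. Their intervals will be wide, so they should be labelled descriptive. Specifying them now avoids presenting the same split later as a post hoc subgroup.

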5.2 EXCLUSION CRITERIA

In order to be eligible to participate in this study, an individual must not meet any of the following criteria:

1. Current or prior treatment with rituximab, belimumab or any other biologic agent in the 6 months prior to screening.
2. Current treatment with methotrexate, azathioprine, mycophenolate mofetil, cyclosporine, tacrolimus, or other less common immunomodulatory drugs such as those falling into the class of disease-modifying antirheumatic drugs (DMARDs), not otherwise specified herein. Participants previously on methotrexate, azathioprine, mycophenolate mofetil, cyclosporine or tacrolimus, or other DMARDs should have withdrawn drug for at least 8 weeks (56 days) at the time of screening.
3. Treatment with cyclophosphamide, pulse methylprednisolone or IVIG within 6 months prior to screening.
4. Current treatment with potent inhibitors of Cytochrome P450 3A4 (CYP3A4) (e.g., ketoconazole) or receiving one or more concomitant medications that result in both moderate inhibition of CYP3A4 and potent inhibition of CYP2C19 (e.g., fluconazole) that would increase serum availability of Tofacitinib. Past treatment with the aforementioned agent is allowed if it was more than a week prior to the administration of the first dose of study medication.
5. History of chronic liver disease, not including well-controlled Sjogren's-related chronic liver disease or elevated LFTs:
 - ALT or AST \geq 2x upper limit of normal at screening
 - Serum unconjugated bilirubin $>$ 2mg/dL at screening
6. Serum creatinine $>$ 1.5mg/dL.
7. Protein to creatinine ratio of more than 1mg/dL at screening (repeated and confirmed three times or confirmed with 24 hours urine protein of more than 1000 mg).
8. Active urinary sediment (WBC, RBC or mixed cellular casts 1+ or more /hpf).
9. Hypercholesterolemia: Values after 8-12 hour fasting blood specimen: total cholesterol $>$ 250 mg/dL or LDL $>$ 180 mg/dL or hypertriglyceridemia (triglyceride $>$ 300 mg/dL) within - 45 days of screening visit.
10. WBC $<$ 2500/ μ L or ANC $<$ 1,000/ μ L, Hgb $<$ 9.0 g/dL or platelets $<$ 70,000/ μ L or absolute lymphocyte count $<$ 500/ μ L.
11. Pregnant or lactating women. Women of childbearing potential are required to have a negative pregnancy test at screening.
12. A history of drug or alcohol abuse within the 6 months prior to screening.
13. Currently receiving hemodialysis, peritoneal dialysis, or intestinal dialysis.
14. Active infection that requires the use of oral or intravenous antibiotics unresolved at least 14 days prior to the administration of the first dose of study medication.
15. Active chronic infections including but not limited to HIV, Hepatitis B, Hepatitis C, and BK viremia at screening visit.

16. Current or previous diagnosis of malignant disease, except for basal cell or squamous cell carcinoma of the skin with complete excision and clear borders or adequately treated in situ carcinoma of the cervix.
17. Known active tuberculosis. Participants with treated latent tuberculosis (LTB) will be eligible to participate. Participants with untreated LTB will not be excluded but will be evaluated by an infectious disease (I.D.) consultant and may become eligible for trial based on infectious disease consultant recommendations.
18. History of severe or systemic infection caused by common pathogens, or history of infection with pathogens that normally do not cause human disease.
19. Participants with active renal or central nervous system disease or a high activity level in any organ system (except articular) in ESSDAI⁵⁴.
20. Participants with known increased risk factors for major adverse cardiac event (MACE) including a history of:
 - Ischemic heart disease (e.g., history of acute myocardial infarction)
 - Heart failure
 - Cardiomyopathy
 - Severe valvular heart disease
 - Significant arrhythmias
 - Chronic renal failure
 - Cerebrovascular accident or transient ischemic attack
 - Uncontrolled diabetes mellitus
 - Uncontrolled hypertension
 - Current smokers or former smokers with less than 3 years since complete cessation and/or >20 pack-years of smoking history.
21. Significant impairment of major organ function (lung, heart, liver, kidney) or any condition that, in the opinion of the Investigator, would jeopardize the participant's safety following exposure to the study drug.
22. Known history of arterial or venous thrombosis or at high risk for clotting disorder
23. Psychiatric illness or history of medical non-compliance that the study team feels will make the patient unlikely to complete the study
24. Uncontrolled thyroid disease as per PI or medically responsible investigator.
25. Known allergic reactions to Tofacitinib or its components
26. Treatment with another investigational drug/intervention within six months except for COVID-19 vaccines or therapies that have been granted an FDA emergency authorization.

5.3 INCLUSION OF VULNERABLE PARTICIPANTS

We do not intend to enroll the following vulnerable populations: children, pregnant women, prisoners, or decisionally-impaired adults.

Spanish speakers and patients who speak other languages may be eligible for participating in this study. We will use a Spanish translated version of the long form for enrollment of Spanish speaking participants. NIH translators will be provided at study appointments.

5.3.1 Participation of NIH Staff or family members of study team members

NIH staff and family members of study team members may be enrolled in this study as long as this population meets the study entry criteria. Neither participation nor refusal to participate as a subject in the research will have an effect, either beneficial or adverse, on the participant's employment or position at NIH.

We will follow the requirements outlined in Policy 404 Research Involving NIH Staff as Subjects, ensuring the guidelines (<https://policymanual.nih.gov/3014-404>) are met.

Every effort will be made to protect participant information, but such information may be available in medical records and may be available to authorized users outside of the study team in both an identifiable and unidentifiable manner.

The NIH Frequently Asked Questions (FAQs) for Staff Who are Considering Participation in NIH Research will be made available. Please see section 10.1.1 for consent of NIH Staff Lifestyle Considerations.

During this study, participants are asked to:

- Fast overnight (past midnight) for the following visits: Screen, Day 1, Day 84, Day 168 and Day 196.
- Withhold salivary stimulants for 24 hours prior to saliva collection.
- Refrain from eating or drinking anything for 1 ½ hours prior to having a saliva collection. Saliva collection is done at the following visits: Screen, Days 1, 84, 168 and 196.

